- Demographics: Age, sex, race/ethnicity
- Pre-existing medical conditions
- Concomitant medications
- Vital signs including height, weight, calculated body mass index (BMI)
- CDI History, including:
 - o Date of initial CDI diagnosis
 - Number of CDI recurrences since initial diagnosis
 - o Baseline clinical symptoms and severity related to CDI
 - CDI treatments received to date

Section 2: FMT Procedure

- Study patient identifier
- Date
- Description of FMT procedures, including:
 - Route of administration (colonoscopy/sigmoidoscopy or enema)
 - Location in colon where FMT delivered
 - Sedation (if applicable)
 - Prep quality (if applicable)
 - Findings of colonoscopy (if applicable)
- Dose
- Unit ID/Lot# of each treatment
- Expiration Date
- Storage Condition
- FMT retention time (if less than 1 hour)
- Immediate adverse events

2. Short-term assessment I (Day 3 – Telephone Assessment)

- Study patient identifier
- Date
- Any change in baseline clinical symptoms related to CDI
- Assessment of SAEs, including:
 - Any complications related to FMT administration
 - Any potential infectious complications such as transmissible enteric infections, sepsis, peritonitis, or bacteremia
 - Any non-serious newly diagnosed infections (specific organism and body site)

- Any new medical conditions / new medications with associated clinical course
- Any changes in pre-existing medical conditions with associated clinical course
- 3. Short-term assessment II (Week 6 Clinical Assessment)
 - Study patient identifier
 - Date
 - Vital signs including height, weight, calculated body mass index (BMI)
 - Any change in baseline clinical symptoms related to CDI including documentation of clinical cure or clinical non-response
 - Assessment of SAEs, including:
 - Any complications related to FMT administration
 - Any potential infectious complications such as transmissible enteric infections, sepsis, peritonitis, or bacteremia.
 - Any new non-serious diagnosed infections (specific organism and body site)
 - Any new medical conditions / new medications with associated clinical course
 - Any changes in pre-existing medical conditions with associated clinical course

4. Long-term assessment I (Month 6 – Telephone Assessment)

- Study patient identifier
- Date
- Self-reported height and weight, resulting calculated BMI
- Any recurrence of CDI with description of clinical course, including additional treatments received
- Assessment of any new SAEs

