• The AE is more likely explained by FMT than by another cause

VI-E. Reporting Safety Observations by the Investigator to the Sponsor

1. Reporting of Non-serious AEs

All AEs, regardless of seriousness, severity, or causal relationship to FMT, will be recorded in the AE section of the subject case report form.

2. Reporting of FMT Exposure during Pregnancy

If a female subject or the female partner of a male subject becomes pregnant during the course of study, the Investigator must report this occurrence to the Sponsor within **72 hours** of becoming aware of the pregnancy. The Investigator is required to follow up on the pregnancy until it has completed. The outcome of the pregnancy and the status of the newborn (if applicable) will be reported within 24 hours of becoming aware. If the female partner of a male subject becomes pregnant, the Investigator must obtain consent to collect pregnancy information (including the status of the newborn, if applicable).

3. Reporting of Safety Observations by the Investigator

Any occurrence of the following events or outcomes must be reported expeditiously by the Investigator or qualified designee to the local IRB and to the Sponsor, who will be responsible for reporting the event to the FDA:

- 1. SAE related to FMT material
- 2. Death of a subject related to FMT material

The site Investigator is to report any safety observations from the list above to the Sponsor within **72 hours** of becoming aware of the event, who in turn, will notify the FDA. Any observation that is also an AE will be recorded on the subjects case report form along with any actions taken. If not all information is available at the time of initial report, follow up SAE reports will be completed and submitted.

Any occurrence of the following events or outcomes must be reported by the Investigator or qualified designee to the local IRB and to the Sponsor, who will be responsible for reporting the event to the FDA:

- 1. SAE unrelated to FMT material
- 2. Death of subject unrelated to FMT material
- 3. Hospitalization related to CDI
- 4. New or worsening medical condition, or new medications

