The Investigator is to report any safety observations from the list above to the Sponsor within **7 days** of becoming aware of the event. The Sponsor will notify the FDA in its Annual Report. Any observation that is also an AE will be recorded on the subjects case report form along with any actions taken. If not all information is available at the time of initial report, follow up SAE reports will be completed and submitted.

The site Investigator is required to follow SAEs until resolution, regardless of whether the subjects are still participating in the study. Resolution is defined as:

- Resolved with or without residual effects
- Return to baseline for a pre-existing condition
- Fatal outcome; if autopsy is performed, the autopsy report must be provided to the Sponsor.

VI-F. Monitoring the study database and submitting safety reports

The Sponsor will notify FDA of any unexpected fatal or life-threatening suspected adverse reaction related to FMT material as soon as possible, but no later than 7 calendar days after the Sponsor's initial receipt of the information. The Sponsor will notify the FDA and all participating Investigators in an IND safety report of potentially serious risks from this study as soon as possible, but no later than 15 calendar days after the Sponsor receives the safety information and determines that the information qualifies for reporting. Participating Investigators include all Investigators enrolling subjects under the Sponsor's IND. In addition, the Sponsor will identify in each IND safety report, all IND safety reports previously submitted to FDA concerning a similar suspected adverse reaction and will analyze the significance of the suspected adverse reaction in light of previous, similar reports or any other relevant information. The Sponsor will evaluate a suspected adverse reaction in the context of other related reports or adverse events. The Sponsor will periodically review and analyze the entire safety database, for IND safety reporting purposes, and also to update Investigator brochures with new safety information. An IND safety report will be submitted when any of the following criteria are met:

A. Serious and unexpected suspected adverse reaction related to FMT material

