A serious and unexpected adverse reaction is a SAE as determined by the Investigator or Sponsor, as defined previously, in combination with unexpected, defined as not being listed in the Investigator Brochure. At the request of the FDA, it will also include any documented infectious disease, defined as a new onset infection in the recipient after FMT and the infection present in the safety aliquot, which is a sample of the exact specimen that was transferred to the patient.

B. Findings from other sources

The Sponsor will also expeditiously report any findings from clinical, epidemiological, or pooled analysis of multiple studies or any findings that

suggest a significant risk in humans exposed to FMT and thought related to the material.

C. Increased occurrence of serious suspected adverse reactions related to FMT material

The Sponsor will report any clinically important increase in the rate of a serious suspected adverse reaction over that listed in the protocol.

VI-G. Halting Rules

Specific safety findings will result in temporarily suspending enrollment until a safety review is convened, the objective of which is to determine whether the study should continue per protocol, proceed with caution, be further investigated, be discontinued, or be modified and then proceed. Suspension of enrollment, for a particular group, such as colonoscopy group, or for the entire study, is another potential outcome of a safety review.

Subsequent review of serious, unexpected, and related AEs by the Data and Safety Monitoring Board (DSMB), IRB, the Sponsor, or the FDA or relevant local regulatory authorities may also result in suspension of further trial interventions/administration of FMT at a site. The FDA and study Sponsor(s) retain the authority to suspend additional enrollment and study interventions/administration of FMT for the entire study, as applicable.

Findings that will trigger a safety review are

- Death related to FMT material
- Confirmed transmission of a clinically concerning infection from donor to subject via FMT
- If one or more subjects experiences a serious, unexpected adverse event related to FMT material
- Significant increase in frequency of events theoretically related to FMT material (specifically, new diagnoses of inflammatory bowel disease). Discussion on threshold will be discussed with DSMB and will be on a disease specific basis.

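### The 72-hour reporting list in VI-E.3 omits the infection class that VI-F.A makes IND-reportable and that VI-G can make a halting trigger

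*Combined protocol and SAP*

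**What the plan says.** Section 6 (Protocol) deals with an infection passed on in the donor material in several places.

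- **VI-F.A** widens the class of events that call for an IND safety report to "any documented infectious disease, defined as a new onset infection in the recipient after FMT and the infection present in the safety aliquot". Seriousness is not a condition. VI-F sets the sponsor's limit for an IND safety report at "no later than 15 calendar days after the Sponsor receives the safety information and determines that the information qualifies for reporting".
- **VI-G** lists "Confirmed transmission of a clinically concerning infection from donor to subject via FMT" among the findings that trigger a safety review, with enrollment suspended until the review is held. It does not require an SAE, and it does not define which infections are clinically concerning.
- **VI-E.3** gives the investigator two lists. The 72-hour list has two items: "SAE related to FMT material", and death with the same relationship. The 7-day list has SAEs and deaths unrelated to the material, hospitalization for CDI, and "New or worsening medical condition, or new medications". For the 7-day list, "The Sponsor will notify the FDA in its Annual Report".
- **VI-E.1** has every AE entered on the case report form and sets no reporting time.
- **VII-E** keeps expedited FDA reporting for unanticipated serious events related to the material and sends anticipated and less serious events to the IRBs and FDA annually.

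Under Data Collection in Section V, the Day 3 and Week 6 forms already ask for new non-serious infections by organism and body site. The baseline form records the Unit ID or lot number.

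**The concern.** The sponsor can act on VI-F.A and VI-G only after a site has told it about an infection. The list meant to bring urgent events to the sponsor does not name that infection. Two kinds of case miss the 72-hour route: a non-serious infection, and an infection of any seriousness that the investigator does not yet judge related to the material.

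The second kind involves a circularity. VI-D.2 calls an event related only if FMT explains it better than another cause does. The best evidence for that is a match in the safety aliquot. The aliquot can be tested on account of a particular infection only after someone reports that infection.

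Donor-to-recipient transmission is the risk named in the SA1 and SA2 hypotheses. Section IV describes the donors as universal, so an index case may bear on other recipients of the same donor. Under VI-F, participating investigators learn of such a risk through the IND safety report, which cannot be prepared until the sponsor has heard from the site.

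**Working it through.** The plan gives no figure to reproduce. The check traces the event through the sections and compares the time limits.

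**Route of a new infection, by how the investigator classes it**

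| Investigator's classification | VI-E list | Time to sponsor | FDA route in VI-E |
|---|---|---|---|
| SAE, related to material | First | 72 hours | Sponsor notifies FDA |
| SAE, not judged related | Second | 7 days | Annual Report |
| Non-serious, related or not | Second, as a new condition or medication | 7 days | Annual Report |

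VI-F.A states that the reportable class is extended: "At the request of the FDA, it will also include any documented infectious disease, defined as a new onset infection in the recipient after FMT", provided the infection is also in the aliquot. Rows two and three can therefore become 15-day events once a match is found, yet VI-E describes them as Annual Report items. VII-E repeats the annual route for less serious events and makes no exception for a matched infection.

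**Delay at the site-to-sponsor step**

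- Inputs: 72 hours and 7 days (VI-E.3).
- 7 × 24 − 72 = 96 hours = 4 days.

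**Longest chain to an IND safety report**

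- Input: 15 days (VI-F), taking the event to qualify on the day of receipt.
- Through the 72-hour list: 3 + 15 = 18 days.
- Through the 7-day list: 7 + 15 = 22 days.
- The time needed to test the aliquot is not stated and would add to both chains.

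**Study doses given during the 4 days**

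- Inputs: 150 subjects and an estimated study duration of 24 months (VII-A). The accrual period is not stated, so 12 to 24 months is assumed, with uniform accrual and one first dose per subject.
- 12 months: 150 / 365.25 = 0.411 per day; × 4 = 1.6 doses.
- 24 months: 150 / 730.5 = 0.205 per day; × 4 = 0.8 doses.

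These doses come from all donors. Those from the donor in question would be some part of them.

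**The case against.** The strongest reply is that the sections work in sequence and do not conflict. VI-E governs what the investigator sends to the sponsor, and its Annual Report sentence is the default for routine items. VI-F.A is a separate sponsor duty that begins once a match is known, and nothing in VI-E cancels it. This largely stands as an account of the sponsor's obligations. It does not remove the inconsistency on the page, because no section says that a matched infection leaves the Annual Report route. It also does not explain why the site step should be slower for this class.

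Other safeguards also count:

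- The SAE definition in VI-A includes important medical events that need no hospital admission. The Day 3 and Week 6 forms place transmissible enteric infections under the assessment of SAEs. Some outpatient infections will therefore be SAEs and, if judged related, will take the 72-hour route.
- The sponsor periodically reviews the whole safety database (VI-F), and telephone follow-up data are entered in the database at once (Section VIII).
- The DSMB may meet outside its quarterly schedule (VII-E).
- If the study is halted for review, FDA is told within 48 hours (VI-G), so notice of a halt is not annual.
- What prompts aliquot testing may be set out in the OpenBiome Master File, which the protocol cites but does not reproduce. It cannot be called missing.

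A reader might infer that the halting trigger could fail to fire at all, or that exposure should be counted over a full quarter until the next DSMB meeting. The documents do not support either. The 7-day report is mandatory and has no seriousness or causality filter for a new condition or medication, and the form entry in VI-E.1 is an added duty, not an alternative to it. A reader might also infer that every non-serious transmitted infection halts enrollment; VI-G is limited to clinically concerning ones.

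**Conclusion.** The point holds as a gap in the reporting route with a small stated delay. VI-E.3 leaves out of its 72-hour list an infection class that VI-F.A makes reportable and that VI-G may act on. The FDA route that VI-E.3 and VII-E give for such an event is inconsistent with the 15 days in VI-F for an aliquot-matched infection. The delay written into the text is 4 days at the site-to-sponsor step, about 0.8 to 1.6 study doses from all donors. The dose figure rests on uniform accrual over an assumed 12 to 24 months. It is not a count of doses avoided, because testing time is unknown and the VI-G trigger needs confirmed transmission.

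The point is more than one of wording because the 72-hour rule depends on a relatedness judgment for which the best evidence usually comes later. The protocol already applies 72 hours to pregnancy (VI-E.2), which it states is not an AE, so a short limit without a seriousness or causality test is not foreign to the plan.

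**What to change.** Reconcile VI-E.3, VI-F.A, VI-G and VII-E as follows.

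1. Add a third item to the 72-hour list in VI-E.3: new-onset infection that could have been transmitted by FMT material, regardless of seriousness or assessed causality.
2. State that receipt of such a report prompts the sponsor to have the safety aliquot for that Unit ID tested, or cross-refer to the Master File if it already covers this.
3. State in VI-E.3 and VII-E that a positive match follows VI-F.A, and VI-G where applicable, rather than the Annual Report.
4. Have the sponsor define what VI-G means by a clinically concerning infection.

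The cost is a few lines of text and a notice to sites, then a few more 72-hour reports and occasional aliquot tests. The Day 3 and Week 6 forms need no new items for this.

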Although the efficacy of FMT appears convincing, there is a paucity of robust safety data for FMT. The current safety profile has been collected predominantly from retrospective reviews or systematic reviews of case series data, approaches that have methodological limitations in assessing the safety of FMT.^{21 24 25} Broadly, the literature contains inconsistent long-term follow-up of adverse events, which have been spontaneously reported rather than actively sought, in turn increasing the risk of underreporting. ²¹ Randomized controlled trials have also had brief follow-up and one trial was stopped early for benefit at interim analysis, limiting the ability to meaningfully assess the long-term safety profile of FMT.^{22 23} Although the current body of literature does not signal any significant safety risk for FMT, a high-quality prospective longitudinal study is needed to confirm the safety profile of FMT among recurrent CDI patients.

OpenBiome is a 501 (c) (3) non-profit organization that is the first public FMT stool bank in the United States for CDI non-responsive to standard therapy. Under the FDA's current regulatory framework of enforcement discretion, OpenBiome has partnered with more than 100 health care institutions in over 30 states to expand safe, affordable access to FMT. Accordingly, our institute is uniquely positioned to meaningfully assess the safety profile of FMT, as our group and others have identified an absence of high-quality, prospective studies interrogating safety.²¹

II. General Investigational Plan

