- Any new medical conditions / new medications with associated clinical course
- Any changes in pre-existing medical conditions with associated clinical course

5. Long-term assessment II (Month 12 – Telephone Assessment)

- Study patient identifier
- Date
- Self-reported height and weight, resulting calculated BMI
- Any recurrence of CDI with description of clinical course, including additional treatments received
- Assessment of any new SAEs
- Any new medical conditions / new medications with associated clinical course
- Any changes in pre-existing medical conditions with associated clinical course

Data Analysis

Primary Study: Safety and Efficacy (Aims 1-3)

Safety endpoints will be collected with raw events and crude rates reported for overall cohort. Clinical cure rates will be calculated at each site. Both unweighted pooled clinical cure rates and weighted pooled clinical cure rates will be calculated with corresponding 95% confidence interval (CI) for overall study, as well as pre-defined

subgroups including: age, gender, modified Horn index, delivery modality, donor, retention time, site. Weighted pooled rates will be analyzed using the random effects model (DerSimonian-Laird method). Heterogeneity across sites will be assessed using the I² statistics and the Cochran Q test, where I² > 50% or Cochrane Q < 0.10 will be considered to indicate significant heterogeneity. Statistics will be performed using Stata SE 12.0 (StataCorp, College Station, TX).

Secondary Study: Microbiome (Aim 4)

DNA will be extracted from each frozen specimen collected from both donors and recipients. The V4 region of the 16S rRNA gene will be amplified using multiplexed bar-coded primers as previously described.²⁷ Up to 192 samples will be pooled onto a single lane of an Ilumina MiSeq for high-throughput sequencing. Quality trimmed and filtered sequence data will be clustered into Operational Taxonomic Units (OTUs) for computational analysis. Each recipient will receive an engraftment score based on their similarity (as quantified by the Jensen-Shannon Divergence) to the donor used in their FMT. Recipients will also be assessed for the long-term stability of their community and it's similarity to samples collected and previously published from both healthy and dysbiotic patients.

VI. Adverse Event Monitoring

We will capture both short and long-term safety profiles, including:

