 - Mild: Transient or intermittent episodes of unformed stools OR increase of ≤3 stools over baseline per 24-hour period
 - Moderate: persistent episodes of unformed to watery stools OR increase of 4-6 stools over baseline per 24-hour period
 - Severe: Bloody diarrhea OR increase of ≥7 stools per 24-hour period OR IV fluid replacement indicated

- Potentially Life Threatening: Life-threatening consequences (e.g. hypotensive shock)
- Nausea
 - Mild: Transient (<24 hours) or intermittent nausea with no or minimal interference with oral intake
 - Moderate: Persistent nausea resulting in decreased oral intake for 24-48 hours
 - Severe: Persistent nausea resulting in minimal oral intake for >48 hours OR aggressive rehydration indicated (intravenous fluids)
 - Potentially Life Threatening: Life-threatening consequences (e.g. hypotensive shock)
- Vomiting
 - Mild: Transient or intermittent vomiting with no or minimal interference with oral intake
 - Moderate: Frequent episodes of vomiting with no or mild dehydration
 - Severe: Persistent vomiting resulting in orthostatic hypotension OR aggressive rehydration indicated (intravenous fluids)
 - Potentially Life Threatening: Life-threatening consequences (e.g. hypotensive shock)

Long-term

The following long-term AEs and relevant details will be solicited:

- Gastrointestinal disorders
 - Inflammatory bowel disease
 - Irritable bowel syndrome
 - Celiac disease
 - Colon cancer
- Chronic infectious diseases (no therapy, outpatient, inpatient, ICU care)
- Autoimmune diseases
 - Inflammatory arthritis
 - Thyroid disease
 - Connective tissue diseases
 - Idiopathic thromobocytopenic purpura
- Metabolic disease
 - Diabetes Type 2 (diet controlled, oral hypoglycemic, insulin, uncontrolled/complication associated)
 - Metabolic syndrome (including obesity independently)
 - Non-alcoholic fatty liver disease
- Neuro-psychiatric disease
 - Multiple sclerosis
 - Depression/Anxiety
- Cardiovascular disease
 - Myocardial infarction (NSTEMI/STEMI)

- Stroke
- Cardiovascular related death

VI-C. Monitoring of Adverse Events

Each subject will be monitored for the occurrence of AEs, including SAEs. Each subject will be followed for safety monitoring at each follow-up interval.

- Subjects will be questioned at each follow-up interval regarding stool
 patterns, abdominal pain, fevers, and subjective well-being. First, subjects
 will be questioned about the possible occurrence of adverse events in a

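### After Week 6 no listed item asks directly about acute non-serious infection or requires the organism, although the safety-aliquot reporting rule has no time limit

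*Combined protocol and SAP*

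**What the plan says.** All places are in Section 6 of the combined protocol and SAP unless stated.

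- **Reporting rule (VI-F, part A).** At the FDA's request, IND safety reports also cover any documented infectious disease, "defined as a new onset infection in the recipient after FMT and the infection present in the safety aliquot". The sentence stands under a heading on serious reactions, but it extends that category and sets no condition of seriousness or time.
- **Safety-review trigger (VI-G).** One trigger is "Confirmed transmission of a clinically concerning infection from donor to subject via FMT". It has no time limit either.
- **Early contacts (V, Data Collection).** Day 3 lists "Any non-serious newly diagnosed infections (specific organism and body site" and Week 6 lists "Any new non-serious diagnosed infections (specific organism and body site". Both also list potential infectious complications.
- **Late contacts (V, Data Collection).** Month 6 and Month 12 list "Assessment of any new SAEs", CDI recurrence, changes in pre-existing conditions, and "Any new medical conditions / new medications with associated clinical course". Neither infection item is repeated.
- **Long-term solicited list (VI-B).** The only infection entry is "Chronic infectious diseases (no therapy, outpatient, inpatient, ICU care". It grades by level of care and does not mention the organism.
- **Manner of asking (VI-C).** Stool pattern, abdominal pain, fever and well-being are to be asked about at every follow-up. A general question comes first, and the solicited questions follow only if the answer is positive.

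**The concern.** The reporting rule runs for the whole study, but the data item that feeds it is listed only up to Week 6. To apply the rule one needs to know that an infection occurred and which organism caused it.

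Two things depend on this. First, SA2 concerns long-term safety, and its hypothesis is that donor screening keeps donor-to-recipient transmission low. Data Analysis (V) reports raw events and crude rates. If infections are asked about specifically before Week 6 and only generally afterwards, a lower late count partly reflects the change in questions.

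Second, the organism decides the reporting route. A late non-serious infection logged only as a new condition goes to the sponsor within 7 days and to the FDA in the Annual Report (VI-E). The same infection, once matched to the aliquot, qualifies for an IND safety report within 15 days of the sponsor's receiving the information and finding it reportable (VI-F). If nobody establishes the organism, the slower route applies by default.

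**Working it through.** The plan gives no figure on this point, so there is none to reproduce. The check compares the contact lists and then does arithmetic on the schedule.

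**1. Items by contact (V, Data Collection)**

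| Item | Day 3 | Week 6 | Month 6 | Month 12 |
|---|---|---|---|---|
| Infectious complications | yes | yes | no | no |
| Non-serious infections, organism and body site | yes | yes | no | no |
| SAEs | yes | yes | yes | yes |
| New conditions / new medications | yes | yes | yes | yes |
| Changes in pre-existing conditions | yes | yes | yes | yes |

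At the early contacts the two infection items are sub-items of the SAE assessment. At the late contacts the SAE line stands without sub-items. Severe complications such as sepsis would normally still qualify as SAEs, so the real loss is the non-serious item and its organism field.

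**2. Time after the last infection-specific contact.** Inputs: Week 6 and Month 12 (week 52), each +/- 2 weeks (Baseline assessment and follow-up).

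- Nominal: 52 − 6 = 46 weeks; 46/52 = 88.5%.
- Shortest: 50 − 8 = 42 weeks; 42/50 = 84%.
- Longest: 54 − 4 = 50 weeks; 50/54 = 93%.

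**3. Recall periods at nominal visits**, with Month 6 taken as week 26.

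- Day 3 to Week 6: 6 − 3/7 = about 5.6 weeks, with infection items.
- Week 6 to Month 6: 26 − 6 = 20 weeks, without them.
- Month 6 to Month 12: 52 − 26 = 26 weeks, without them.

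**4. What is left uncovered.** Serious infections fall under the SAE item, chronic infections under the VI-B long-term list, and CDI under the recurrence item. What remains is acute, non-serious, non-CDI infection with onset after Week 6. The general questions can pick it up, but no listed item asks for it by name or requires the organism.

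**5. Number affected.** The documents give no background infection rate. As an assumption for scale only, if 10% to 30% of the 150 subjects had at least one diagnosed non-serious infection in that period, 150 × 0.10 = 15 to 150 × 0.30 = 45 subjects would have an event for which no listed item requires the organism. These would be background infections, not transmissions, and most would be unrelated to FMT.

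**The case against.** A reader might infer that late infections are left to whatever subjects choose to mention. The documents do not support that. A study representative calls at Month 6 and Month 12 and asks about any new condition and any new medication, and VI (item 4) says this information is elicited. A diagnosed infection is a new condition, and an antibiotic for it is a new medication. Fever, stool pattern and abdominal pain are to be asked about at each interval (VI-C). Subjects are told to report any adverse event, and all AEs are recorded (VI-E). The protocol faults earlier literature for events "spontaneously reported rather than actively sought, in turn increasing the risk of underreporting"; scheduled calls with broad questions are better than that.

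A reader might also infer that no late infection could ever be compared with the aliquot. That does not follow either. Suspected AEs go to the site investigator, who decides on assessments and laboratory tests, and the results are filed in source documents (VI-C). An organism may emerge that way.

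The narrowing also looks deliberate: VI separates solicited short-term events from a long-term focus on new conditions and medications. VI-D ties relatedness to a reasonable time frame, which a minor infection months after FMT will seldom meet. VI-G is limited to clinically concerning infections.

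Most of this stands. It shows that capture exists, and that the 46 weeks do not all carry equal risk of transmission. It does not show that late capture is as specific as early capture, or that anyone is required to obtain the organism. Nor does VI-F part A carry the time frame or clinical-concern qualifier that would justify narrower questions.

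**Conclusion.** The point holds as an inconsistency in ascertainment that is cheap to repair. A rule without a time limit is supported by infection-specific questions that end at Week 6. For nominally 46 of 52 weeks (42 to 50 across windows), acute non-serious infection is reached only through general questions recalled over about 20 and 26 weeks, and a match to the aliquot depends on the investigator's work-up.

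This does not invalidate the safety assessment, and it does not show that any transmission would be missed. The number of subjects affected is unknown.

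The conclusion rests on two assumptions. One is that the contact lists in Data Collection reflect the case report forms; Appendix 4 is not in the text available here, so the Month 6 and Month 12 forms could not be checked. The other is that VI-F part A is meant to apply throughout follow-up, as its wording implies.

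**What to change.** - In Data Collection, add the two Week 6 infection items to the Month 6 and Month 12 lists: infectious complications, and non-serious diagnosed infections with organism and body site. Add date of onset.
- State in VI-C that these are direct questions, asked whatever the answer to the opening general question. Otherwise changing the VI-B list alone would not ensure that they are asked.
- In the VI-B long-term list, change the entry to *Infectious diseases (acute or chronic)*.
- If the Appendix 4 forms already carry these items, only the text of Data Collection, VI-B and VI-C needs aligning with them.

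The cost is two existing items repeated at two existing contacts: a slightly longer call and more background infections on record, most of them unrelated to FMT. In return, the infection questions and the organism field are the same across the whole period covered by SA2 and the aliquot rule.
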